### 10.4 Populations for Analysis

### 10.4.1 Per Protocol Set (PP)

Randomized subjects who terminated the study and in whom no major protocol violations have been observed.

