### 4.5 Study Duration

The primary endpoint will be assessed 6 months  $\pm$  7 days after sinus floor elevation. The entire study duration for each enrolled subjects is 9-14 months (screening to last visit).

The entire study duration from first patient in until last patient out will be approximately 17 months.

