### 8 Study conduct

#### 8.1 Visit Windows

The goal should always be to keep the given time point of each visit. However the time windows given below are the limits to be kept to perform according to the protocol.

Visit 0	Visit 1	Visit 2	Visit 3	Visit 4	Visit 5	Visit 6
Informed Consent	Screening Visit	Sinus elevation (Baseline)	Wound healing assessment	Implant placement	Wound healing assessment	Initial implant loading
28-2 days before screening	14-0 days before Baseline	Day 0	Day 7-14	6 months ± 7 days	2 weeks after visit 4	4 months ± 1 month after visit 4

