### 10.2 Statistical Hypotheses

The primary endpoint of this study is the histological evaluation of the ratio of newly formed bone to residual bone graft in *Straumann*® *VivOss*™ compared to *Geistlich Bio-Oss*® at visit 4 (6 month ± 7 days, after sinus elevation).

In this study the following hypothesis will be tested

Straumann® VivOss™ combined with Bio-Gide shows a significantly higher ratio of newly formed bone to residual bone graft compared to Geistlich Bio-Oss® combined with GeistlichBio-Gide at visit 4 (6 month ± 7 days, after sinus elevation).

- T: Test Group
- C: Comparator Group

Testing for Superiority (based on the per protocol (PP) data set):

 $H_{0S}$ : T = C

 $H_{1S}$ :  $T \neq C$ 

 $H_{0S}$  is the null hypothesis, claiming that there is no difference in the true mean of ratio of newly formed bone to residual bone graft after 6 months between the test group and the negative control group

H1S is the alternative hypothesis claiming that the true mean change of ratio of newly formed bone to residual bone graft after 6 months is unequal in the two treatment groups; either higher or lower in the test group than in the negative control group.

- T is the true mean at 6 months of the ratio of newly formed bone to residual bone graft in the test group.
- C is the true mean at 6 months of the ratio of newly formed bone to residual bone graft in the control group.

The secondary efficacy variables in this clinical study are:

- Survival rate of study implants evaluated at visit 6 (initial implant loading)
- Success rate of study implants evaluated at visit 6 (initial implant loading)

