### 10.3 Sample Size Calculation

Sample size calculations were performed for a clinical relevant difference between test and comparator across a given range of standard deviations, and with the two-sided unpaired t-test under a significance level  $\alpha = 5\%$  and with a power  $\beta = 80\%$ .

a) Sample Size for Test to Show Superiority of Test Group vs. Control Group

Version 6.0 Page 30 of 47

Based on a recent pre-clinical study a difference of the means of the ratio of newly formed bone to residual bone graft of approximately 0.4 can be expected in favour of the test treatment compared to the control. Considering a common standard deviation of 0.5, 25 subjects per group would be necessary to confirm this clinically relevant difference statistically.

Table 1: Sample size for superiority based on  $\Delta = 0.4$ :

Common SD [mm]	0.425	0.45	0.475	0.5	0.525	0.55	0.575
n Test	18	20	23	25	28	30	33
n Control	18	20	23	25	28	30	33

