### 10.4.2 Full Analysis Set (FA)

This data set will include all randomized subjects who have received at least one study device and from whom at least one measurement of post randomization data is available. It will include subjects even with major protocol violations and premature termination. The FA Set includes the PP Set.

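### The per-protocol set used for the primary test has no cutoff visit, so events after the six-month biopsy can remove an evaluable core from that test

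*Combined protocol and SAP*

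**What the plan says.** - **Primary test.** Section 10.2 attaches the hypothesis test to one data set: "Testing for Superiority (based on the per protocol (PP) data set". The outcome is the ratio of new bone to residual graft "at visit 4 (6 month ± 7 days, after sinus elevation".
- **PP set.** Section 10.4.1 gives a single definition: "Randomized subjects who terminated the study and in whom no major protocol violations have been observed". It names no visit, puts no time limit on violations, and does not vary by endpoint.
- **FA set.** Section 10.4.2 draws a contrast: "It will include subjects even with major protocol violations and premature termination". No primary or sensitivity test is assigned to this set anywhere in section 10.
- **Timing.** Section 4.5 places the primary assessment at six months after sinus floor elevation and describes the subject's time on study as follows: "The entire study duration for each enrolled subjects is 9-14 months (screening to last visit". Section 8.1 puts Visit 6, the last visit, at "4 months ± 1 month after visit 4".
- **Numbers and replacement.** Sections 4.4 and 5.4 plan 25 subjects per group, the same number that section 10.3 calculates. Section 4.4 plans three months of recruitment. Section 8.4 replaces a subject who falls out of the PP population only while recruitment is open.

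**The concern.** The primary measurement is physically complete at Visit 4. The core has been taken and fixed (section 7.14), and nothing that happens to the subject afterwards can change its histology. A membership rule that looks past Visit 4 can therefore only take valid primary data out of the comparison.

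Two things are at stake. The first is precision, in a trial whose enrolment equals its calculated sample size. The second is that the primary comparison becomes conditional on events that follow the outcome in an open-label study. Section 8.3 lets the investigator withdraw a subject for non-compliance or for an adverse event that prevents further participation, and both can occur between Visit 4 and Visit 6.

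**Working it through.** **Step 1. What *terminated* means.** Two readings are possible.

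- *Completed the study.* The FA definition is said to keep subjects with premature termination. That addition has a purpose only if the PP set leaves them out. With section 4.5 running the study to the last visit, completion means reaching Visit 6.
- *Ended the study for any reason.* Section 8.2 uses the study termination form for screening failures, and section 8.5 uses it for subjects lost to follow-up. On this usage, a subject lost after Visit 4 has also terminated, and the criterion would exclude almost nobody.

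The first reading is the likelier one, but it is an inference.

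**Step 2. Who leaves the primary test under each reading.**

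| Event between Visit 4 and Visit 6, evaluable core in hand | Terminated = completed | Terminated = ended for any reason |
|---|---|---|
| Lost to follow-up or withdrawn | out of PP | stays in PP |
| Major protocol violation | out of PP | out of PP |

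The second row does not depend on the word at all, because section 10.4.1 puts no time limit on violations.

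**Step 3. Length of the exposed interval.** 4 − 1 = 3 months to 4 + 1 = 5 months after Visit 4.

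**Step 4. Can the losses be replaced?** The first subject reaches Visit 4 six months (± 7 days) after surgery. Planned recruitment lasts three months. If that timetable is kept, recruitment has closed before any Visit 4 takes place, so section 8.4 cannot make up a loss after Visit 4.

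**Step 5. Reproducing the plan's sample size.** Inputs from section 10.3: difference 0.4, SD 0.5, two-sided 5%, power 80%.

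n per group = 2 × [SD × (z₀.₉₇₅ + z₀.₈₀) / difference]² = 2 × [0.5 × (1.960 + 0.842) / 0.4]² ≈ 24.5, rounded up to 25.

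This matches the plan, and the same formula reproduces all seven entries of its Table 1. It is the normal approximation with no allowance for dropout. The t-test that the plan names needs 26 per group.

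**Step 6. Power of the t-test as cores are lost.** The noncentrality is 0.4 / [0.5 × √(1/n₁ + 1/n₂)] on n₁ + n₂ − 2 degrees of freedom, two-sided 5%.

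| Cores in test / control | Noncentrality | Power |
|---|---|---|
| 25 / 25 | 2.828 | 79.1% |
| 25 / 24 | 2.799 | 78.3% |
| 24 / 24 | 2.771 | 77.4% |
| 23 / 23 | 2.713 | 75.6% |

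One core lost in total costs a little under 1 point. One lost in each arm costs 79.1 − 77.4 = 1.7 points, and two lost in each arm cost 79.1 − 75.6 = 3.5 points. The documents give no dropout rate, so these rows are scenarios and not forecasts.

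**The case against.** **The text never says Visit 6.** This is correct. A reader might infer that the protocol openly requires attendance at Visit 6 for the primary test. It does not: that follows from the FA contrast and the study duration, and the protocol's own forms use the word more loosely. A clear definition could also fix the cutoff at Visit 4. What remains is that the cutoff is unstated and that the violation criterion reaches past Visit 4 on either reading.

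**The cores are not discarded.** This is also correct. A reader might infer that these biopsies vanish from the trial, but they stay in the FA set. The gap is that no test is assigned to that set. Nor does the protocol say that one PP set serves every endpoint: section 10.2 ties it to the superiority test only, and no set is named for implant survival or success.

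**The bias is speculative.** This stands. A reader might infer that failed implants, and so poor grafts, are filtered out of the primary test. Implant failure is an outcome assessed at Visit 6, not a listed reason for withdrawal or a violation, so a subject with a failed implant who attends remains eligible. Nothing in the documents shows that later losses would be common, unequal between arms or related to the ratio. In a deliberately extreme simulation with no true difference (SD 0.5, 25 per group), removing the one, two or three lowest ratios from one arm only raised the type I error from 5% to about 6.5%, 9.6% or 13.4%. That is a worst case, not a prediction.

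**Losses may be few.** This is plausible: Visit 6 is when the implant is loaded, so subjects have a treatment reason to attend.

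**The later SAP may settle it.** Section 10 promises a SAP finalized after the data review meeting and before database lock. It is not in the documents, so it neither cures nor confirms the problem. A rule chosen that late in an open-label trial is also weaker than one in the protocol.

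**Conclusion.** The point holds as a defect in the membership rule, modest in size and cheap to remove. If section 10.4.1 is followed as written, a major violation after Visit 4 takes an evaluable core out of the primary test. On the likelier reading of *terminated*, loss or withdrawal after Visit 4 does the same. Such losses come straight out of a sample with no reserve and cannot be replaced on the planned timetable.

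The cost is about 1 point of power for one core lost in total and 1.7 points for one lost in each arm. These figures rest on the plan's difference and SD and on an assumed number of losses. The shortfall from 80% at 25 per group is a separate matter: it comes from the normal-approximation sample size. Any link between later losses and graft quality is hypothetical, so the documents do not support a claim that the primary comparison is biased.

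**What to change.** In section 10.4.1, and in the SAP when written:

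1. For the ratio endpoint, define the PP set as randomized subjects with an evaluable Visit 4 core and no major violation up to and including Visit 4.
2. State that later events do not remove a subject from the primary test, unless consent to use the tissue or data is withdrawn (paragraph 25 of the Declaration in Appendix 1 bears on this).
3. Require follow-up to Visit 6 only for the implant survival and success analyses.
4. Prespecify the same test on all FA subjects with an evaluable core as a sensitivity analysis.

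This takes a few sentences and no extra visits or data. The downside is that the PP sets for the ratio and for the implant endpoints may differ by a few subjects, which the report would have to show. The change does not settle whether a PP set should carry a superiority claim at all. If the FA set became primary, most of this point would fall away.

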### 10.4.2 Full Analysis Set (FA)

This data set will include all randomized subjects who have received at least one study device and from whom at least one measurement of post randomization data is available. It will include subjects even with major protocol violations and premature termination. The FA Set includes the PP Set.

### 10.4.3 Safety Analysis Set (SA)

This data set will include all subjects who have received at least one study device. The SA Set includes the FA Set.

#### 10.4.4 Not Treated (NT)

Subjects enrolled in the study who did not receive the study device will be excluded from the analysis.

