### 4.3 Study Treatments

Before entering into the study, each subject has to sign an informed consent. A subject is enrolled if she/he meets all inclusion criteria and at the same time does not meet any exclusion criteria. Enrolled subjects will be scheduled for sinus elevation. At surgery subject eligibility will again be evaluated according to secondary exclusion criteria. Subjects who do not meet any secondary exclusion criteria are randomized to one of the following groups:

- a) Sinus floor elevation with Straumann® VivOss™
- b) Sinus floor elevation with Geistlich Bio-Oss®

After a healing time of 1-2 weeks, sutures are removed, and the wound healing is evaluated. After a healing time of 6 months, an intermediate osteotomy for the dental implant placement is done by means of a trephine burr in such a way that the biopsy is harvested at the same time. Dental implant placement will be completed according to the standard procedure of the clinic. After a healing time of 1-2 weeks, the sutures are removed and the wound healing is evaluated. 4 months after implant placement the implant is initially loaded and the survival as well as the success rate will be evaluated.

Version 6.0 Page 14 of 47

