### 5.3 Secondary exclusion criteria at sinus floor elevation

If the following criteria is met at sinus floor elevation, the subject must be excluded from the study:

1. Defects of the Schneider Membrane

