### 8.2 Screening Failures

Any subject that has signed the informed consent form, is not randomized and does not receive the study device is considered a screening failure. In the event of a screening failure, the case report forms should be completed up to the visit when the subject was determined to be a screening failure. The "study termination form" should also be completed and a new subject should be recruited if the recruitment period is ongoing.

In case of a screening failure according to an eligibility criterion that may be re-evaluated at a later time point (e.g. oral hygiene), a re-screening of the patient is possible as judged by the investigator if the recruitment period is ongoing. In this case, a "re-screening form" should be completed instead of the "study termination form".

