#### 9.2 Adverse Event (AE)

Any untoward medical occurrence, unintended disease or injury or any untoward clinical signs (including an abnormal laboratory finding) in subjects, users or other persons whether or not related to the investigational medical device.

NOTE 1: This includes events related to the investigational device or the comparator.

NOTE 2: This includes events related to the procedures involved (any procedure in the clinical investigation plan).

NOTE 3: For users or other persons this is restricted to events related to the investigational medical device.

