#### 9.3 Expected adverse events

The following adverse events (irrespective of relatedness) can be expected:

- General risks that exist with dental surgical procedures: Bleeding and bruising, pain and swelling after the surgical procedure. Infections in the soft and hard tissue, delayed healing, recession of the gum and/or bone, temporary or permanent nerve damage in the jaw, oro-sinus or oro-nasal fistulas and possible rejection are very rare.
- The following are examples of complications that can generally occur with a surgical procedure using implants and can therefore not be completely ruled out:
  - Slight pain and tenderness the first days after surgery

Version 6.0 Page 24 of 47

- Slight swelling and redness the first days after surgery
- Gingival inflammation (oral hygiene dependent): Oral hygiene instructions are given and oral hygiene procedures performed to prevent gingival inflammation. The occurrence of gingival inflammation will be monitored by means of the modified gingival index and if it occurs the investigator will provide treatment as needed and repeat oral hygiene instructions.
- General risks that exist with a surgical procedure using barrier membranes and can therefore not be completely ruled out: soft tissue dehiscence (tissue damage), haematoma, pain, increased sensitivity and redness due to inflammation.

In regard to wound healing assessments only clinically significant symptoms that are outside the normally accepted range (as judged by the clinician) will be reported as adverse events. This includes, but not restricts to:

- Excessive or progressively increasing pain or discomfort
- Excessive swelling
- Signs of infection (e.g. suppuration)
- Wound / soft tissue breakdown (e.g. soft tissue necrosis, flap dehiscence)
- Any other condition or observation deemed outside of the normal range of healing characteristics

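### Subjects excluded for a membrane defect after study surgery has begun have no scheduled adverse event recording after Visit 2 and enter no planned safety summary

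*Combined protocol and SAP*

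**What the plan says.** Section 4.3 applies the term enrolled before surgery: "A subject is enrolled if she/he meets all inclusion criteria and at the same time does not meet any exclusion criteria". Eligibility is checked again at the operation, and "Subjects who do not meet any secondary exclusion criteria are randomized to one of the following groups". Section 5.3 names one secondary criterion, a defect of the Schneider membrane, and makes it binding: "If the following criteria is met at sinus floor elevation, the subject must be excluded from the study".

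Section 8.2 defines the status of anyone who stops before allocation: "Any subject that has signed the informed consent form, is not randomized and does not receive the study device is considered a screening failure". For such a subject "the case report forms should be completed up to the visit when the subject was determined to be a screening failure", and a study termination form is filed.

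Section 10.4.3 builds the safety set from subjects who received at least one study device. Section 10.4.4 adds: "Subjects enrolled in the study who did not receive the study device will be excluded from the analysis". It makes no exception for safety.

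The adverse event definition in section 9.2 is wider than device use. Its second note reads: "This includes events related to the procedures involved (any procedure in the clinical investigation plan"). The Schedule of Assessment places adverse event recording at Visits 2 to 6, with the first wound check (Visit 3) on day 7-14.

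**The concern.** Section 8.2 makes no distinction between a subject who fails an entry criterion at the screening visit and one whose sinus operation has already started. The second has been exposed to a protocol procedure and can have complications of it. Several of the surgical risks in section 9.3, such as infection, delayed healing and soft tissue dehiscence, would usually show themselves after the day of surgery, and the first scheduled look for them is Visit 3. A subject whose CRF closed at Visit 2 does not reach it.

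At stake is the absolute account of procedural safety. Read as written, the plan's adverse event summaries describe graft recipients only, and a reader could take them as describing everyone who had the operation.

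**Working it through.** **The rules in sequence, for a subject with a membrane defect**

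1. The subject meets the entry criteria, so is enrolled (4.3).
2. Sinus elevation begins and the defect is found; exclusion is mandatory (5.3).
3. The subject is not randomised (4.3) and receives no device, so is a screening failure (8.2).
4. CRFs run to Visit 2 only (8.2), so the adverse event recording scheduled for Visits 3 to 6 does not take place.
5. With no device the subject is outside the safety set (10.4.3). Being enrolled but without the device, the subject is also removed from the analysis (10.4.4).

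**What the other provisions cover**

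| Provision | Covers | Leaves open |
|---|---|---|
| Schedule, Visit 2 | Events seen on the day of surgery | Anything new afterwards |
| 9.13 | Follow-up of an event that has occurred, to resolution or steady state; screening failures not exempted | Scheduled contact to detect a new event |
| 9.12 | Any serious event the investigator learns of | New non-serious events |
| 8.3 | Adverse event follow-up of subjects the investigator withdraws | Whether exclusion for a membrane defect is such a withdrawal |
| 11.1.1 | CRF data for all who consented | How far the CRF runs, which 8.2 sets |

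None of these puts an event in such a subject into a safety summary.

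**How many subjects**

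The only plan figure used is the 50 to be randomised (sections 4.4 and 5.4). It reproduces from section 10.3. With difference 0.4, SD 0.5, two-sided alpha 5% and power 80%, n per group = 2 × (1.960 + 0.842)² × 0.5² / 0.4² = 24.5, rounded up to 25. All seven columns of Table 1 reproduce the same way. The point here does not depend on that calculation.

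The documents give no membrane defect rate p, so p is an assumption. Operations started to randomise 50 = 50/(1 − p), rounded up. Subjects affected = that number minus 50.

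| Assumed p | 50/(1 − p) | Operations started | Affected | Share of those operated |
|---|---|---|---|---|
| 5% | 52.6 | 53 | 3 | 5.7% |
| 10% | 55.6 | 56 | 6 | 10.7% |
| 20% | 62.5 | 63 | 13 | 20.6% |
| 30% | 71.4 | 72 | 22 | 30.6% |

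**Order of events**

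The synopsis lists randomisation before the secondary exclusion criteria at Visit 2, and heads those criteria as applying during or following surgery. The Schedule of Assessment also shows randomisation and augmentation above them. Section 4.3 puts the check first. If a subject were randomised and then excluded without a device, section 8.2 would not apply, yet section 10.4.4 would still remove that subject. If the device had been placed, the subject would be in the safety set. The passages must be reconciled.

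**The case against.** The strongest reply is that the existing rules may already catch these subjects. A membrane defect arising at surgery could itself be a procedure-related adverse event under section 9.2. It would then be recorded at Visit 2 and followed under section 9.13. It could also count under section 8.3 as an event preventing further participation, which would trigger adverse event follow-up. This reading is possible, so it would be wrong to say flatly that later complications are not collected. But the protocol does not say that a defect is to be logged as an adverse event, nor whether 8.2 or 8.3 governs. Even on this reading, sections 10.4.3 and 10.4.4 keep the events out of the safety analysis.

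A second reply is that section 10 promises a detailed SAP that could add a listing, that the objective is histological, and that section 6.1.3 describes standard procedures with CE-marked products. A device-recipient safety set does suit a comparison of two devices, and an overall procedural event rate is not an endpoint. These points limit the importance. They do not close the gap, because section 10.4.4 as written has no safety exception and a later SAP cannot recover events that nobody was scheduled to record.

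A reader might also infer that events are lost precisely where they are most likely. The documents do not support that: they give neither a defect rate nor a complication rate by membrane status, and of the more serious complications section 9.3 says only that "oro-sinus or oro-nasal fistulas and possible rejection are very rare".

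**Conclusion.** The point holds in limited form. For subjects excluded at surgery for a membrane defect, new non-serious events after Visit 2 have no scheduled collection, and no adverse event of theirs enters a planned safety summary. The procedural adverse event picture therefore covers graft recipients only. With an assumed defect rate of 5% to 30%, this concerns about 3 to 22 operated subjects; the rate is illustrative and has no source in the documents.

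A reader might infer bias between the arms. Under section 4.3 there is none from this source, because the exclusion precedes allocation; the primary comparison and the sample size stand. That conclusion rests on the section 4.3 order, which the synopsis does not match. The matter should be corrected, but its effect is confined to absolute procedural safety reporting.

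**What to change.** 1. Reconcile section 8.2 with 8.3, and the synopsis and schedule with 4.3, so that the protocol says which rule governs an exclusion made during surgery.
2. For these subjects, keep adverse event recording open for a stated period covering the existing Visit 3 window (day 7-14). Use the existing form and whatever post-operative contact the centre's standard of care provides; no new clinical visit is implied.
3. Limit section 10.4.4 to the efficacy analyses.
4. Beside the by-arm safety set, add one listing of membrane-defect exclusions and of adverse events among all subjects in whom sinus elevation was started, with that number as the denominator.

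The cost is a few sentences, one listing and a few more adverse event pages. The overall procedural event rate may look less favourable. Treatment, sample size and the primary test are unchanged.
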